# 1. TRIAL SUMMARY

Title	Randomised clinical trial testing a 1-week course of curative whole breast radiotherapy against a standard 3-week schedule in terms of local cancer control and late adverse effects in patients with early breast cancer.							
Aim	To identify a 5-fraction schedule of curative radiotherapy delivered in 1 week that is at least as effective and safe as the UK standard 15-fraction regimen after primary surgery for early breast cancer.							
Eligibility Criteria	
 
Inclusion criteria (all the following must be met):
 
age ≥18 years
 
female or male
 
invasive carcinoma of the breast
 
breast conservation surgery or mastectomy (reconstruction allowed but not with implant. Tissue expanders with distant metal ports are allowed)
 
axillary staging &/or dissection
 
complete microscopic excision of primary tumour
 
pT1-3 pN0-1 M0 disease
 
written informed consent
 
able to comply with follow up
 
N.B. Concurrent trastuzumab and hormone therapy is allowed
 
							
	
 
Exclusion criteria (the patient is ineligible if any of the following are met):
 
past history of malignancy except (i) basal cell skin cancer and CIN cervix uteri or (ii) non-breast malignancy allowed if treated with curative intent and at least 5 years disease free
 
contralateral breast cancer, including DCIS, irrespective of date of diagnosis
 
breast reconstruction using implants
 
concurrent cytotoxic chemotherapy (sequential neoadjuvant or adjuvant cytotoxic therapy allowed)
 
radiotherapy to any regional lymph node areas (excepting lower axilla included in standard tangential fields to breast/chest wall)
 
							
Study Design	Prospective randomised controlled clinical trial.							
Trial Treatment	Patients are randomised to 15 or 5 daily fractions (Fr) to the whole breast or post-mastectomy chest wall. A sequential tumour bed boost may be added after breast conservation surgery, but dose level (10 Gy or 16 Gy in 2.0 Gy Fr) must be declared before randomisation. Each patient will be allocated to one of the following groups:  Control: 40.05 Gy in 15 Fr of 2.67 Gy  Test 1: 27.0 Gy in 5 Fr of 5.4 Gy							
	Test 2 : 26.0 Gy in 5 Fr of 5.2 Gy							
Endpoints	Primary endpoint: ipsilateral local tumour control Secondary endpoints: early and late adverse effects in normal tissues, quality of life, contralateral primary tumours, regional and distant metastases and survival.							

	]
Sample Size	The sample size is 4,000 patients, with numbers balanced equally in each randomised group. This provides 80% power (1-sided $\alpha$ = 0.025 to allow for 1-sided hypothesis and multiple testing) to exclude an increase of 1.6% in the 5-year local relapse rate between each test group and the control, assuming a 5-year rate of 2% in the 40.05 Gy schedule. Stratification will be by centre and risk group (high- < 50 years or grade 3 vs. low - $\geq$ 50 years and grade 1 or 2). For the photographic, quality of life studies, 2196 patients would provide 80% power to detect an 8% difference in the prevalence of late adverse effects at 5 years between the test groups (assuming a 5-year rate of 35%). Acute toxicity will be monitored in the first 150 or so patients in the trial, to exclude a rate of RTOG grade $\geq$ 3 acute skin reactions of over 11% (89% power and 7.9% significance).
Follow Up	Clinical follow up is as per local practice with annual follow up for recurrence for at least 10 years from date of randomisation.
	Acute toxicity will be assessed by a healthcare professional in the first 150 patients recruited to the trial using a modified RTOG grading system. This will be carried out weekly during radiotherapy and for 4 weeks after treatment. If symptoms persist the patients will be assessed weekly until their reaction settles to RTOG grade 1 or less.
Photographic study	Photographs will be taken at baseline and at 2, 5 and 10 years post randomisation in centres with local facilities. This study will start once the acute toxicity study has finished/ 150 patients have been recruited to the trial.
Quality of Life Study	Quality of Life (QL) will be assessed using the EORTC QLQ-C30 v3.0, EORTC BR23 breast cancer module, BIS and HADS scales and the EORTC FA-13 fatigue module. This study will start once the acute toxicity study has finished/ 150 patients have been recruited to the trial.
	QL questionnaires will be completed at baseline, 3 and 6 months, 1, 2, 5 and 10 years post randomisation.
	The QL study will be undertaken in a subset of centres in the trial. All patients in these centres will be asked to take part in the QL study.
Translational Studies	All patients will be asked to consent to donate a single blood sample and complete a family history questionnaire. This can be collected at any point during the trial.
	Patients will also be asked to consent to the donation of a tissue sample should a recurrence occur. A sample of the original tumour will also be collected at this time.

#### 2. BACKGROUND

The international standard regimen for whole breast radiotherapy delivers a total dose of 50 Gy in 25 fractions (daily doses) over 5 weeks following surgical resection of primary tumour in women with early breast cancer. Attempts to reduce the number of fractions in the 1970s made inadequate downward adjustments to total dose, resulting in unacceptable rates of late complications [1]. These miscalculations inhibited further research in breast radiotherapy fractionation for decades, but interest in fewer larger fractions delivered over a shorter overall treatment time has been rekindled by randomised clinical trials based on a better understanding of normal tissue and tumour responses. Four randomised trials involving a total of >8000 women have compared a lower total dose in fewer larger fractions against 50 Gy in 25 fractions, and all have reported favourable results in terms of local tumour control and late adverse effects [2-6].

The Royal Marsden Hospital/Gloucestershire Oncology Centre and Ontario trials totalling 2644 women with mainly axillary node negative tumours < 5 cm diameter were the subject of a 2008 Cochrane review of altered radiotherapy fractionation in early breast cancer [7]. Radiotherapy fractions larger than 2.0 Gy did not appear to affect: a) local-recurrence free survival (absolute difference 0.4%, 95% CI -1.5% to 2.4%), b) breast appearance (risk ratio (RR) 1.01, 95% CI 0.88 to 1.17; p = 0.86), c) survival at five years (RR 0.97, 95% CI 0.78 to 1.19; p = 0.75), d) late skin toxicity at five years (RR 0.99, 95% CI 0.44 to 2.22; p = 0.98, or e) late radiation toxicity in subcutaneous tissue (RR 1.0, 95% CI 0.78 to 1.28; p = 0.99). The review concluded that the use of unconventional fractionation regimens did not affect breast appearance or toxicity, nor appear to affect local cancer relapse. The results of the UK START trials (N = 4451) were published too late to be included in the overview, but were consistent with the findings. The UK START A trial (N=2236) showed that the estimated absolute differences in 5-year local-regional relapse rates compared with the control schedule of 50 Gy in 2.0 Gy fractions were 0.2% (95% CI -1.3% to 2.6%) after 41.6 Gy and 0.9% (95% CI -0.8% to 3.7%) after 39 Gy. In START A, photographic and patient selfassessments suggested lower rates of late adverse effects after 39 Gy than with 50 Gy, with a hazard ratio for late change in photographic breast appearance of 0.69 (95% CI 0.52 to 0.91, p=0.01). In the UK START B trial (N = 2215) the estimated absolute difference in 5-year local-regional relapse rates for 40.05 Gy compared with 50 Gy was -0.7% (95% CI -1.7% to 0.9%), and the hazard ratio for late change in photographic breast appearance was 0.83 (95% CI 0.66 to 1.04). i.e. the START trials reported similar local tumour control with some evidence of lower rates of late adverse effects

after schedules with fraction sizes larger than 2.0 Gy compared with the international standard 25-fraction regimen [6].

A 15-fraction schedule is now the UK standard recommended by the National Institute for Health and Clinical Excellence (NICE), but it is unlikely to represent the useful limits of hypofractionation for whole breast radiotherapy. There is a history of prescribing once-weekly fractions of whole breast radiotherapy for women too frail or otherwise unable to attend for conventional schedules. In a French series of 115 patients undergoing primary radiotherapy without surgery for non-metastatic breast cancer from 1987 to 1999, the whole breast was treated with 2 tangential fields and received 5 once-weekly fractions of 6.5 Gy [8]. 101 were given additional tumour bed boost doses, 7 with 1 fraction, 69 with 2 fractions and 25 with 3 once-weekly fractions of 6.5 Gy using electrons. Kaplan-Meier estimates of late effects in the breast were 24% grade 1, 21% grade 2 and 6% grade 3 at 48 months. The 5-year local progression-free rate was 78% (95% CI: 66.6-88.4). In a separate French series, 5 once-weekly fractions of 6.5 Gy to the whole breast with no boost were given to 50 women after local tumour excision [9]. Grade 1 or 2 induration was reported in 33% of the patients at a median follow up of 93 months (range 9-140). The 7-year local relapse free survival was 91%. Five fractions of 6.5 Gy are equivalent to 62 Gy in 31 fractions assuming  $\alpha/\beta$  = 3.0 Gy, a significantly higher dose intensity than conventional schedules deliver.

The UK FAST Trial (N = 915) tested two dose levels of a 5-fraction regimen delivering 1 fraction per week against a control schedule of 50 Gy in 25 fractions, defining radiotherapy adverse effects as the primary endpoint [10]. The two test dose levels delivered 5 fractions of 5.7 Gy or 6.0 Gy (total dose 28.5 Gy or 30 Gy), estimated to be iso-effective with the control regimen assuming  $\alpha/\beta$  values of 3.0 Gy or 4.0 Gy, respectively. 915 patients were recruited from October 2004 - March 2007. Mean age was 62.7 years. Only 17 patients (5.2%) developed moist desquamation (12 after 50 Gy, 3 after 30 Gy, 2 after 28.5 Gy) out of 327 with RTOG skin toxicity data available. At a median follow up of 28.3 months (IQR 24.1-33.6), 729 patients had 2-year photographic assessments available, with mild and marked change in breast appearance in 19.3% and 1.7% after 50 Gy, 26.2% and 9.3% after 30 Gy, and 20.3% and 3.7% after 28.5 Gy. Risk ratios for mild and marked change for 30 Gy vs. 50 Gy were 1.48 (95%Cl 1.06 -2.05) and 6.06 (2.14 -17.20), p<0.001 for trend, favouring 50 Gy; and for 28.5 Gy vs. 50 Gy were 1.07 (0.75 -1.54) and 2.25 (0.70 -7.18), p=0.26 for trend, favouring 50 Gy. Any clinically-assessed moderate/marked adverse effects in the

breast were increased for 30 Gy compared with 50 Gy (hazard ratio, HR 2.19, 95%Cl 1.46 - 3.29, p<0.001), but similar for 28.5 Gy (HR 1.33, 95%Cl 0.86 -2.08, p=0.19). At a median follow-up of 37.3 months 2 local tumour relapses had been recorded.

A gain in local tumour control due to shortening treatment time to 1 week is possible. Evidence based on retrospective studies for an influence of treatment time on local tumour control is conflicting with recent systematic reviews drawing different conclusions [11, 12]. Even without a gain in tumour control, accelerated radiotherapy is likely to be more convenient for patients, and may ease scheduling with other treatment modalities. A pilot study (N = 30) tested 30 Gy in 5 fractions of 6.0 Gy in 15 days to the whole breast in terms of acute adverse effects and late effects at 2 years [13]. In this series, 23/30 (77%) patients scored no change in post-operative breast appearance at 2 years, 7/30 (23%) scored mild change and none scored marked change. The acute skin reactions were mild, with no reaction more severe than grade 2 erythema, scored in 9/30 (27%) patients. If the results of the proposed randomised trial support a 5fraction schedule delivered in 1 week, these will transform international breast radiotherapy practices. In conclusion, it is fair to say that after decades of resistance to evaluating larger radiotherapy fraction sizes in breast cancer, expert opinion is responding to an accumulating body of evidence supporting the safety and effectiveness of this approach.

Against this background, a phase III randomised trial is described with the primary aim of testing local tumour control in women with early breast cancer following a 5-fraction schedule of adjuvant radiotherapy delivered in 1 week. Stratification by treatment centre and by local relapse risk will ensure balanced trial groups (high risk defined as patient age <50 and/or grade 3 tumour; low risk defined as age ≥50 and grade 1 or 2 tumour) [14].

#### 3. AIM

To identify a 5-fraction schedule of curative radiotherapy delivered in once-daily fractions, that is at least as effective and safe as the current UK standard 15-fraction regimen after primary surgery for early breast cancer, in terms of local tumour control, adverse effects and quality of life (QL).

#### 4. TRIAL DESIGN

FAST-Forward is a multicentre phase III randomised controlled trial.

#### 4.1 Trial Schema

#### **Patient Population**

[figure not shown]
Female or male, age ≥ 18; primary breast conservation surgery or mastectomy of invasive carcinoma with complete microscopic resection; whole breast/chest wall radiotherapy +/-tumour bed boost dose.

#### **Exclusion Criteria**

- Previous malignancy (other than basal cell skin cancer and CIN cervix uteri), or 5 years disease free following treatment with curative intent.
- · Contralateral breast cancer, including DCIS, irrespective of date of diagnosis.
- · Concomitant chemotherapy (sequential chemotherapy allowed).
- · Radiotherapy to lymphatic pathways.

# Patient eligible for FAST Forward and consents to participate

Baseline Quality of Life questionnaires – **prior to randomisation**Baseline photographs of breast/chest wall following surgery – **prior to radiotherapy**Blood sample collection/family history questionnaire – **at any time** 

\*16 Gy or 10 Gy in 2 Gy fractions sequential electron or photon boost to the tumour bed is allowed in all 3 treatment arms (boost decision to be declared before randomisation for each individual patient)

#### Follow up

Acute toxicity assessments in the first 150 patients - weekly during and for 4 weeks post radiotherapy, then weekly until RTOG ≤1if symptoms persist

\*Quality of Life questionnaires at: 3 & 6 months, 1, 2, 5 and 10 years post radiotherapy

\*Photographs of breast/chest wall at 2, 5 and 10 years post radiotherapy

Tissue collection from primary and recurrence/new primary in either breast

Follow up annually for 10 years post radiotherapy

\* - to start once 150 patients have been recruited to the trial

#### 5. ENDPOINTS

# 5.1 Primary Endpoint

Ipsilateral local tumour control.

# 5.2 Secondary Endpoints

- Acute adverse effects
- Late adverse effects in normal tissues assessed by physicians and patients, including quality of life and photographic assessments
- Contralateral primary tumours
- Regional and distant metastases
- Overall survival.

#### 6. PATIENT SELECTION AND ELIGIBILITY

#### 6.1 Patient Selection

Women and men with complete microscopic resection of early invasive breast cancer following breast conservation surgery or mastectomy for whom local radiotherapy is recommended (patients undergoing reconstruction are eligible unless they have implants).

#### 6.2 Number of Patients

A total of 4000 patients will be recruited. The proportions of patients accrued in subgroups defined by risk of local recurrence will be monitored during the trial, to ensure reasonable representation of low risk (age  $\geq$ 50 and grades 1 or 2) and high risk (age <50 and/or grade 3).

#### 6.3 Inclusion Criteria

To be eligible, all of the following inclusion criteria must be met:

- age ≥18 years
- female or male
- invasive carcinoma of the breast
- breast conservation surgery or mastectomy (reconstruction allowed, but not with implant. Tissue expanders with distant metal ports are allowed)
- axillary staging &/or dissection
- complete microscopic excision of primary tumour
- pT1-3 pN0-1 M0 disease
- written informed consent

able to comply with follow up

N.B. concurrent trastuzumab and/or hormone therapy are allowed

#### 6.4 Exclusion Criteria

The patient is ineligible if any one of the following exclusion criteria is met:

- past history of malignancy except (i) basal cell skin cancer and CIN cervix uteri or
   (ii) non-breast malignancy allowed if treated with curative intent and at least 5 years disease free
- contralateral breast cancer, including DCIS, irrespective of date of diagnosis
- breast reconstruction using implant
- concurrent cytotoxic chemotherapy (sequential neoadjuvant or adjuvant cytotoxic therapy allowed)
- radiotherapy to any regional lymph node area (excepting lower axilla included in standard tangential fields to breast/chest wall)

#### 7. RANDOMISATION

#### 7.1 Randomisation Procedure

An eligibility checklist must be completed and patient consent obtained prior to randomisation.

To randomise a patient, the appropriate centre staff should telephone the ICR-CTSU randomisation line (see below).

Randomisation [contact] Office Hours: 09:00 – 17:00 Monday-Friday

The following information will be required at randomisation:

- name of centre, consultant and person randomising the patient
- patient's full name, hospital number, date of birth, post code and NHS number
- confirmation that an eligibility checklist has been completed and written informed consent has been obtained
- whether the patient has consented to the treatment side effects study (first 150 patients only)
- whether the patient has consented to photographic assessments (once 150 patients have been recruited to the trial)
- whether the patient has consented to take part in the QL study (once 150 patients have been recruited to the trial)
- whether the patient has consented to blood sample and tissue collection

- whether the patient has consented to the use of information held by the NHS and the General Register Office
- whether a boost is to be given and what dose level

The caller will be given the patient's unique randomisation number (Trial ID) and the treatment allocation. The Trial ID together with the patient's initials, date of birth and hospital number should be used on all Case Report Forms (CRFs).

#### 7.2 Treatment allocation

Treatment allocation will be 1:1:1 and will use computer-generated random permuted blocks. Randomisation will be stratified by centre and risk group.

A fax will be sent to the randomising centre to confirm the trial number and treatment allocation.

#### 8. TRIAL EVALUATIONS

#### 8.1 Tumour-related Endpoints

Ipsilateral tumour relapse and contralateral primary tumour must be confirmed by cytological/histological assessment. Metastases will be determined by an appropriate combination of clinical, haematological, imaging and pathological assessment, recognising that pathological confirmation is not always possible. Patients will have annual clinical assessments for 10 years and annual mammograms for 5 years or until screening age if younger (as per NICE guidelines).

# 8.2 Treatment-related Endpoints

#### 8.2.1. Acute reactions (first 150 patients in the trial)

Acute reactions of the skin of the treated breast will be recorded in the first 150 patients recruited into the trial. This will be assessed as described below.

#### Clinical assessments of acute adverse effects

The acute reactions of the skin of the treated breast will be graded according to the RTOG criteria (Appendix 1) and will be assessed by a healthcare professional at each centre. The assessments will be carried out weekly during treatment and for 4 weeks following the end of radiotherapy. If symptoms persist the assessments will continue weekly until the reaction is RTOG grade 1 or less.

#### Patient self-assessments of acute adverse effects

The patient will be asked to report their own acute toxicity of breast radiotherapy (breast soreness, reddening, swelling and blistering) by completing a diary card weekly during treatment and for 4 weeks after the end of radiotherapy. The scores will be recorded as "none", "a little", "quite a bit" or "very much". If symptoms persist then patients will be asked to continue scoring their adverse effects on a weekly basis until all scores are graded as "none" or "a little".

#### 8.2.2 Late reactions (all patients)

Late adverse effects will be measured using an annual clinical assessment. Late effects will also be measured in a subset of patients using photographic assessments and patient self-assessments from the quality of life questionnaires. Incidence of ischaemic heart disease and second malignancies will also be recorded.

#### Clinical assessments of late adverse effects

At annual visits for 10 years (from date of randomisation into study) physicians will record the development of breast shrinkage/distortion (including reconstructed breasts), breast induration (outside and inside tumour boost volume), breast pain and breast oedema (for patients receiving radiotherapy following breast conserving surgery) and telangiectasia (tumour boost site only), shoulder stiffness (compared with other side), ischaemic heart disease, rib fracture, costochondritis, symptomatic lung fibrosis, persistent cough and any other severe late event, including any specialist referral for investigation or management of late toxicity (for all patients).

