# Photographic assessments of late adverse effects (in all centres with local facilities)

Digital photographs will be taken at baseline (post-surgery but pre-RT) and at years 2, 5 and 10 after radiotherapy. Timing of assessments is based on experience from the START trial, with the aim to maximise the information collected whilst minimising the assessment burden. Two frontal views of the chest will be taken, one with hands on the hips and the other with hands raised as far as possible above the head. Both photographs will exclude the patient's head.

All photographs will be taken and retained locally in the first instance. Digital images will be coded and stored on a CD to be kept in a secure location. Periodically all CDs will be collected by ICR-CTSU and the images assessed blind by a select group of observers. Change in breast/reconstructed breast/chest wall appearance and distortion

compared with the post-surgical baseline will each be scored on a three-point graded scale. Breast size and surgical deficit will each be assessed on a three-point graded scale from the baseline photographs. Reliability and repeatability of the assessments will be verified. The feasibility of and procedures for this scoring mechanism have been established for breast conserving surgery patients in the START trial [15] and assessments for FAST-Forward will build on these existing methods, including validating the method in chest wall patients.

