# 9.2. Schedule of assessments

			Т	reatme	nt				Fo	llow-up	)			
Event	Prior to randomisation	Post randomisation pre RT	wk 1	wk 2	wk 3	Weekly to week 8	mth 3	mth 6	yr 1	yr 2	yr 3	yr 4	yr 5	yr 10
Eligibility checklist	х													
Informed consent	х													
Randomisation checklist	x													
Radiotherapy QA			Prior	to cent	re initia	ition and through	hout the	e trial re	ecruitm	ent pei	riod			
3D radiotherapy planning		х												
Radiotherapy treatment			х	x 	x 									
Radiotherapy verification				p to dai										
Serious Adverse Event (if applicable)			x	x	x	x	x							
Acute toxicity assessments		x (first 150 pts)	х	x	х	х								
Clinical assessment		x (first 150 pts)	x	x	х	x (first 150 pts)	х	х	x	х	х	х	х	x (Annually to yr 10)
Quality of life	x (baseline*)						х	х	х	x			х	х
Photographic assessment		х								х			х	х
Blood sample collection and family history questionnaire		At any time dur	ing the	trial, id	eally b	y the end of RT								
CT scan if recurrence		At the time of recurrence												
Tissue collection - 1° tumour - recurrence/new 1° tumour			As requested during the trial											

\* Follow up booklets will be sent by post from the ICR-CTSU office; Control group only; CRFs to be completed throughout the trial as indicated in the Trial Guidance Notes

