#### 17.2 Methods of Analysis

Survival analysis methods (i.e. Kaplan-Meier analysis and Cox proportional hazards regression) will be used to compare rates of local recurrence between allocated treatments for all randomised patients (i.e. intention to treat). Normal tissue effects will be analysed using methodology developed for the START Trials; i.e. survival analyses of time to occurrence of moderate or marked effects, as appropriate. Analysis of the QL data will follow algorithms developed for the QL forms (i.e. calculation of standardised sub-scale scores), and will compare treatment groups at individual time points, as well as longitudinal changes from baseline. A generalised linear modelling approach will be used to describe the longitudinal QL data, taking into account important prognostic factors such as age, stage of disease, treatment received and other socio-demographic and clinical characteristics. Appropriate adjustments will be made for multiple comparisons in the analysis of the QL data by adopting a more stringent cut-off for statistical significance.

The sample size calculations have been based on survival analysis methods. The 5-year figure has been used as the clinically relevant time point and assumes that recurrences before and after five years will be included in the analysis accordingly (i.e. patients will be followed from randomisation until it becomes impractical to do so further, and patients will only be censored in the analysis upon death or if lost to follow-up). Analyses will incorporate the time to an event as well as the occurrence of that event.

As this is a non-inferiority trial if there is high non-compliance with the test treatment groups then an analysis of only those compliant with the protocol will also be conducted.

The incidence of uncommon serious complications will be monitored.

Analyses of local tumour recurrence and of normal tissue effects adjusting for adjuvant therapy (chemotherapy, hormonal therapy) will be performed. Analyses of normal tissue effects will also be adjusted for breast size and surgical deficit.

Analyses will estimate the size of treatment effect with a confidence interval for the estimated difference between schedules. Information will be provided on both the absolute and relative treatment effect. Each Test group will be compared with the

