#### 18.3 Quality of Life Study

The quality of life study will be implemented once the acute toxicity study has finished i.e. after the first 150 patients have been recruited into the trial.

There is evidence that radiotherapy causes long-term effects on quality of life in terms of altered breast appearance, breast, arm and shoulder symptoms, as well as a possible impact on some general aspects of QL such as fatigue. Results from the START trial have highlighted the value of patients' self-reported post-radiotherapy symptoms in discriminating between RT regimens in favour of hypofractionation [22]. Experience of the START trials showed that patient-rated cancer specific QL data, obtained with the EORTC QLQ-C30 [16] provided useful data at baseline (for example concerning the effects of surgery) [23] and also made a small contribution to a comparison of the regimens up to 2 years, fewer changes in parameters were observed from 2-5 years (unpublished data 2010). The FAST-Forward QL sub study is planned to provide subjective views of key breast symptoms and, body image over 10 years of follow-up and thus to add supportive data in the comparison of a trade off between local tumour control and adverse effects of treatment. The key effects of radiotherapy on QL are hypothesised to be on a range of breast symptoms as reported for the START trial [22] and potentially on body image plus short term general effects such as fatigue. Patient-reported arm and shoulder symptoms associated with RT are expected to be minimal since lymphatic RT is not allowed in the FAST-Forward trial. In the START trials these symptoms largely related to prior surgery [22].

The QL study is detailed in Appendix 4.

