# **Statistical Analysis Plan**

The algorithms developed for use with the QL questionnaires will be used to measure the parameters of interest. Groups of patients will be compared at agreed time points and overall for differences in these parameters [10]. The treatment groups will be compared at the individual time points with appropriate adjustments being made for multiple comparisons. Normal tissue effects will also be analysed using methodology developed for the START Trials i.e. survival analyses of time to occurrence of moderate or marked effects (scored 'quite a bit' or 'very much'). Because of the longitudinal nature of the data, an analysis which takes into account the repeated measures is also needed. A generalised linear modelling approach will be adopted [11-13]. This will allow the appropriate error distribution to be used and will enable the analysis to take account of important factors such as age, stage of disease, treatment received and other socio-demographic and clinical characteristics.

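### No pre-radiotherapy physician score of the late-effect items is scheduled for all patients, so effects left by surgery cannot be separated from new ones and differences between schedules are pulled towards zero

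*Protocol*

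**What the plan says.** Section 8.2.2 sets one late-effect measure for the whole trial: "Late adverse effects will be measured using an annual clinical assessment". Photographs and patient questionnaires cover subsets. Under the heading on clinical assessments, "physicians will record the development of breast shrinkage/distortion (including reconstructed breasts", followed by induration, breast pain, breast oedema, telangiectasia at the boost site, shoulder stiffness judged against the other side, and several rarer events. The scoring takes place at annual visits for 10 years.

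In the Section 9.2 schedule, the clinical assessment cell between randomisation and radiotherapy reads "x (first 150 pts"). The acute toxicity row carries the same restriction in the same column.

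Section 17.2 plans "survival analyses of time to occurrence of moderate or marked effects, as appropriate" and adds: "Analyses of normal tissue effects will also be adjusted for breast size and surgical deficit". The source of those two covariates is in the photographic part of Section 8.2.2: "Breast size and surgical deficit will each be assessed on a three-point graded scale from the baseline photographs".

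For the questionnaires, Appendix 4 says "Normal tissue effects will also be analysed using methodology developed for the START Trials", with an event being an item scored at one of the two highest levels. On the origin of patient-reported arm and shoulder symptoms, Section 18.3 states: "In the START trials these symptoms largely related to prior surgery".

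**The concern.** Recording that something has developed needs a known starting point. All patients have had breast-conserving surgery or mastectomy with axillary staging or dissection (Section 6.3), and surgery can itself leave distortion, induration, oedema, pain and a stiff shoulder. If the first physician score comes after treatment, a patient who was already moderate or marked is an event at the first annual visit in any arm, whatever schedule she received. Judging the shoulder against the other side does not remove this, because the operated side is the irradiated side.

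Such patients carry no information about schedule but add the same amount to each arm's event rate. Absolute differences and ratios both move towards no difference. The aim in Section 3 is a schedule at least as safe as the control, and attenuation makes a real excess of harm harder to see. An uncollected baseline cannot be restored by a later analysis plan, so this belongs to the protocol.

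**Working it through.** **Which items and patients are exposed**

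- Physician items that surgery can also cause: shrinkage/distortion, induration, breast oedema, breast pain, shoulder stiffness. No baseline score is scheduled for all patients.
- Photographs: change is scored against a post-surgical baseline, so they are not affected.
- Telangiectasia, rib fracture and lung fibrosis: not plausibly present after surgery alone, so not affected.
- Questionnaire items: a baseline is collected before randomisation. However, the time-to-event definition in Appendix 4 states no rule for patients already at the event level. Section 17.2 mentions change from baseline only for the longitudinal quality-of-life analysis.

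**Reproducing the plan's nearest figure**

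The protocol gives no power for the physician items. The nearest figure is in Section 17.3.3 and Appendix 4 for the photographic and quality-of-life sub-studies: 732 per group, 80% power, an 8-point difference from 35%, two-sided 0.025, 10% loss. Two proportions of 35% and 27% with continuity correction need 659 per group, and 659/0.9 = 732.2, rounded up to 733. The stated 732 is reproduced within rounding. These rates are borrowed below.

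**Dilution model**

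Inputs: p1 = 0.35 and p2 = 0.27 (planning rates). Evaluable patients per arm n = 4000/3 × 0.9 = 1,200 (Section 17.3.1). Two-sided alpha = 0.025, so z = 2.2414. The share b is moderate or marked from surgery and still so at first scoring, equal in all arms. It is an assumption, shown from 5% to 20%.

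Observed rate = b + (1 − b)p. Observed difference = (1 − b)(p1 − p2).

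Power = Φ[(d − z·SE0)/SE1], where d is the observed difference, SE0 = √(2p̄(1 − p̄)/n), SE1 = √((p1(1 − p1) + p2(1 − p2))/n), p1 and p2 are here the observed rates and p̄ is their mean. No continuity correction is used.

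Example, b = 0.10: rates 0.415 and 0.343, d = 0.072, SE0 = 0.01981, SE1 = 0.01975. Then (0.072 − 2.2414 × 0.01981)/0.01975 = 1.40, giving 92%.

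| b | Observed rates | Difference (points) | Risk ratio | Power, no baseline | Power if baseline-positive patients are identified and excluded, n(1 − b) per arm |
|---|---|---|---|---|---|
| 0 | 35.0% v 27.0% | 8.0 | 0.77 | 98% | 98% (1,200) |
| 5% | 38.3% v 30.7% | 7.6 | 0.80 | 95% | 97% (1,140) |
| 10% | 41.5% v 34.3% | 7.2 | 0.83 | 92% | 96% (1,080) |
| 20% | 48.0% v 41.6% | 6.4 | 0.87 | 82% | 94% (960) |

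The last column uses the same formula with the undiluted 35% and 27%.

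**Does it bias the interpolation between dose levels?**

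On the rate scale the position of the control between the two test doses is (pC − p26)/(p27 − p26). With equal b every difference is multiplied by (1 − b), which cancels. Illustration with assumed rates of 10%, 12% and 15% for 26 Gy, control and 27 Gy: 0.02/0.05 = 0.40. At b = 10% the rates are 19.0%, 20.8% and 23.5%, and 0.018/0.045 = 0.40. On a log-ratio scale the position moves only from ln(1.2)/ln(1.5) = 0.45 to ln(0.208/0.190)/ln(0.235/0.190) = 0.43. Precision falls; the position hardly moves.

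**The case against.** The strongest reply is that the protocol does address surgical state. Section 17.2 adjusts normal tissue analyses for breast size and surgical deficit, and surgical deficit is the main confounder for shrinkage/distortion. This stands in part. Both covariates are read from baseline photographs, which exist only for consenting patients at centres with facilities, after the first 150 have been recruited. Surgical deficit also says little about pain, oedema or a stiff shoulder.

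Second, the late-effect endpoints for which power is stated (photographs and questionnaires) have baselines, so the gap concerns one secondary source. That is true and limits the weight of the point, but the physician score is the only late-effect measure in all patients.

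Third, physicians are asked for development and may know how the patient looked after surgery, and the form is not shown. A reader might infer that surgical effects are certain to be counted as radiotherapy effects; the documents do not support that. They support only that the two cannot be separated from the scheduled data.

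Fourth, a reader might take the schedule to mean that 150 patients have a late-effect baseline and the rest do not. The restricted cell matches the acute toxicity row, and nothing says that late-effect items are scored there.

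Fifth, the size rests on an assumed b, and oedema, pain or stiffness that settles before the first annual visit would not count. Section 18.3 supports a surgical origin only for patient-reported arm and shoulder symptoms. This stands, and is why b is shown as a range.

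**Conclusion.** The point holds for the physician-scored items that surgery can also cause. Without a pre-radiotherapy score in all patients, the planned time-to-first-event analysis cannot tell new effects from old ones, and differences between schedules are pulled towards zero. At the borrowed planning rates the loss of power is slight at b = 5% and clear at b = 20% (98% to 82%); the 8-point difference becomes 6.4 points. These figures assume equal b across arms, as randomisation would give on average, and persistence of the surgical effect to first scoring.

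Two stronger readings should be resisted. One is that the interpolation between test doses is biased: under this model it is unchanged on the rate scale and only less precise. The other is that the test schedules gain a known advantage. No toxicity margin is set, Section 17.2 commits to estimates with confidence intervals, and attenuation would equally hide a true benefit. It is anti-conservative only in the sense that real excess harm is harder to detect.

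**What to change.** 1. In Section 8.2.2 and the Section 9.2 schedule, add one physician score of the same late-effect items after surgery and before radiotherapy for all patients. In Section 17.2, adjust each physician-item analysis for that score, or count an event only when the grade is worse than at baseline, so that worsening in patients already affected is kept.
2. In the Appendix 4 analysis plan, adjust each questionnaire item's time-to-event analysis for its own baseline score.
3. For patients with no baseline physician score, report these items as post-treatment prevalence and not as development.

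Change 1 costs one form page before radiotherapy, and someone able to grade the items must be available then; the protocol does not say who sees patients at planning. Change 2 needs no new data. If baseline-positive patients are excluded instead of adjusted for, fewer remain at risk for that item (960 of 1,200 per arm at b = 20%) and their worsening is lost, so adjustment or a worsening rule is preferable.
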